# **Nutrition ameliorates the muscle loss of pre-sarcopenia in elderly**

## **1. Background and Research Objectives**

Population aging has become a global concern. Taiwan is projected to enter a “super-aged society” by 2025, with individuals aged 65 and above comprising over 20% of the total population (approximately 4.81 million people). Older adults often suffer from degenerative diseases, leading to progressive disability and diminished quality of life and dignity. Among the physiological declines associated with aging, loss of muscle mass is particularly prominent. When accompanied by reduced muscle strength or physical function, this condition is defined as sarcopenia. Sarcopenia has recently been recognized as a geriatric syndrome and is associated with adverse clinical outcomes such as disability, falls, injuries, hospitalization, and poor recovery from illness. It is considered a major contributor to loss of independence in older adults. Currently, there is no definitive clinical biomarker for sarcopenia. Functional assessments often reflect fatigue and frailty but do not necessarily indicate sarcopenia itself.

This subproject will recruit participants from the main integrated aging study and identify individuals with **pre-sarcopenia** for nutritional intervention. We plan to collect blood and urine samples from 120 participants at two time points: mid-intervention (6 weeks) and post-intervention (12 weeks). Functional assessments related to sarcopenia will be conducted after the intervention. Using metabolomics approaches, we aim to evaluate the effectiveness of nutritional supplementation, identify potential biomarkers for risk sarcopenia, and assess their prognostic value. The findings will contribute to understanding the physiological mechanisms of sarcopenia and support future therapeutic monitoring.

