## **2. Experimental design and methods**

**2.1 Study Period:** April 1, 2021 – May 31, 2023

**2.2 Participant Recruitment:** Participants will be recruited from annual health check-ups conducted in Songshan District, Taipei City, and at the Chang Gung Health and Wellness Village. Those enrolled in the main integrated aging study and meeting inclusion criteria will be invited to participate.

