#### **2.5 Sample Size: 120 participants**

#### **2.6 Measurements, Duration, and Risks Study Procedures:**

- 2.6.1 Participants will undergo nutritional assessment via questionnaire and receive a daily supplement containing 8.5 g whey protein and 1.5 g leucine for 12 weeks.
- 2.6.2 At week 6, participants will return for blood (5 mL) and urine (10 mL) collection and report supplement adherence.
- 2.6.3 At week 12, participants will return for a second round of blood and urine collection, supplement adherence assessment, and sarcopenia-related functional tests (body composition, grip strength, walking speed, and calf circumference).

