#### **2.8 Nutritional supplementation**

Participants received sachets containing the nutritional supplement and were instructed to consume two sachets daily over a 12-week intervention period. Each 8 g serving provided 35 kcal, comprising 4.1 g of protein, 1 g of fat, and 2.4 g of carbohydrates. Follow-up assessments were conducted throughout the intervention to monitor adherence. Participants were asked to return both used and unused sachets at each visit, and compliance was defined as consumption of at least 80% of the provided sachets.

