## **2.10 Statistical Analysis**

Metabolomic data will be processed using Topspin and MassLynx for spectral alignment and peak extraction, followed by multivariate analysis with SIMCA-P, including principal component analysis (PCA). Univariate statistical comparisons will be conducted using t-tests and ANOVA for group-level differences. Paired t-tests will be applied to assess within-subject changes before and after nutritional supplementation. Changes in metabolite concentrations in plasma and urine will be linked to individual health indicators to identify biomarkers associated with healthy aging.

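### Everyone is supplemented and no untreated rate of change is estimated, so a before-after paired test cannot support the claim that nutrition lessens muscle loss

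*Combined protocol and SAP*

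**What the plan says.** The title of the combined protocol and SAP is "Nutrition ameliorates the muscle loss of pre-sarcopenia in elderly". Section 1 says of the metabolomics work that "we aim to evaluate the effectiveness of nutritional supplementation", alongside aims on biomarkers and prognosis.

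Section 2.5 sets the size at 120. Under Section 2.6 participants "receive a daily supplement containing 8.5 g whey protein and 1.5 g leucine for 12 weeks", and Section 2.8 says they were "instructed to consume two sachets daily over a 12-week intervention period". No one is described as going without the supplement.

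Section 2.3 admits people who fall below a cut-off on any one of grip strength, walking speed or muscle mass. Section 2.6 lists "sarcopenia-related functional tests (body composition, grip strength, walking speed, and calf circumference" at week 12.

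Section 2.10 states: "Paired t-tests will be applied to assess within-subject changes before and after nutritional supplementation". It also mentions t-tests and ANOVA between groups, but no section defines any groups.

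**The concern.** To say that a loss has been lessened is to compare two rates: loss with the supplement and loss without it. The plan observes only the first. A paired t-test compares the mean change with zero, and zero stands for the untreated course only if untreated people would not change. Section 1 names muscle loss as a prominent decline of aging, so the plan's own premise is that they would.

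The reading of the result is at stake. A flat result could be presented as loss arrested, and a rise as proof of benefit, when neither conclusion follows from the data. A supplement that slowed loss without stopping it would leave a negative mean change and could be written off as a failure.

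**Working it through.** **Inputs from the documents.** One supplemented group of 120 (2.5, 2.6), 12 weeks (2.6, 2.8), a before-after paired t-test (2.10), and entry on at least one low value (2.3). The documents give no significance level, power, effect size, SD, rate of loss or measurement error. The number 120 therefore has no derivation to reproduce. A two-sided 0.05 level is assumed below.

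**Step 1: what the paired contrast estimates.** Write the mean observed change as

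D = U + E + R

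where U is the untreated change over 12 weeks (negative if muscle is being lost), E is the supplement effect, and R is regression to the mean and retest effects. The title's claim concerns E. The design supplies D only. With no estimate of U or R, E is not identified, at any sample size and with any precision of measurement.

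**Step 2: D = 0.** Let the untreated loss be L, so U = -L, and set R = 0.
- Full arrest of the loss: E = L, so D = -L + L = 0.
- No effect, with negligible loss in this interval: L near 0 and E = 0, so D is near 0.

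The same result fits both.

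**Step 3: how a real benefit appears in the test.**
- Full arrest: the true D is 0, so a significant gain appears with probability 0.05/2 = 2.5%.
- Loss halved: the true D is -L + L/2 = -L/2, which is below zero, so a significant gain appears less than 2.5% of the time.

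Neither line needs a value for L.

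**Step 4: how an inert product can appear as a gain.** Take E = 0 and U = 0, and suppose that people enter on a low muscle reading that is also their baseline. With retest correlation rho, share p selected from the bottom of a normal distribution, k the p-quantile, and m = phi(k)/p, in SD units:
- mean rise = (1 - rho) × m
- SD of change = sqrt[(1 - rho)² × (1 - k × m - m²) + 1 - rho²]
- P(significant gain) = 1 - Phi(1.96 - rise/(SD/sqrt(120)))

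Example with rho = 0.90 and p = 0.20: m = 1.400, rise = 0.10 × 1.400 = 0.140, SD = 0.438, SE = 0.438/sqrt(120) = 0.040, ratio 3.50, probability 0.938.

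| rho | p | rise | SD of change | P(significant gain) |
|---|---|---|---|---|
| 0.90 | 0.20 | 0.140 | 0.438 | 0.938 |
| 0.90 | 0.50 | 0.080 | 0.440 | 0.510 |
| 0.95 | 0.20 | 0.070 | 0.313 | 0.687 |
| 0.95 | 0.50 | 0.040 | 0.314 | 0.285 |
| 0.98 | 0.20 | 0.028 | 0.199 | 0.337 |
| 0.98 | 0.50 | 0.016 | 0.199 | 0.139 |

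The values of rho and p are assumptions. The artefact would be smaller if many participants qualified on grip or walking speed instead. It would largely vanish if a fresh baseline were taken after the qualifying reading. Any untreated loss would offset part of it.

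**The case against.** The strongest reply is that the causal claim about muscle sits in the title alone. The stated aims are framed around metabolomics, and none of them names a rate of muscle loss. Section 2.10 opens with metabolomic data and does not name muscle mass as an outcome of the paired test. Section 2.6 lists body composition only at week 12, so a muscle baseline is implied by the entry criteria and not scheduled. All of this is correct. A before-after muscle test is the most favourable reading of the plan; without it, the title has less support still. The reply also leaves the effectiveness aim in Section 1 untouched, because a before-after comparison of metabolites has the same gap.

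A second reply is that between-group tests are planned and that the main aging study might supply comparators. The documents do not rule this out, but they define no groups and describe no unsupplemented data.

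Two stronger readings are tempting and are not supported:
- A reader might infer that the test fails because 12 weeks of loss is about the size of measurement noise. The documents give neither figure. Noise also averages out over 120 people, and Step 1 holds with perfect measurement.
- A reader might infer that Section 1 calls pre-sarcopenia progressive, so that zero must be the wrong reference. That word is applied there to disability. The point needs only that the untreated change is unknown.

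**Conclusion.** The point holds as a mismatch between claim and design. With no unsupplemented participants and no reference rate, the supplement effect is not identified, and this conclusion needs no outside figure. At an assumed two-sided 0.05 level, complete arrest of the loss would show as a significant gain only 2.5% of the time. An inert product could show one in about 14% to 94% of studies, but that range is an illustration. It rests on the assumed retest correlations and selection shares, on entry through the muscle reading, and on that reading serving as baseline.

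This does not make the data worthless. Within-person change over 12 weeks of supplementation can be estimated where both readings exist. It cannot be reported as loss prevented or as a benefit caused by the supplement.

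**What to change.** Restate the title and the effectiveness aim in Section 1 as within-person change over 12 weeks of supplementation. Add three statements to Section 2.10:
- no effect relative to no supplement is estimated;
- no change will not be reported as loss prevented;
- a gain will not be attributed to the supplement alone, given entry on low values and the lack of a comparison group.

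The cost is wording only, with no new visits, participants or assays. The downside is a more modest claim.

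Using each person's earlier check-up slope as the reference in place of zero is not a safe substitute. If the low qualifying reading both ended that slope and served as baseline, selection would exaggerate the earlier decline as well as the later gain, and both errors favour the supplement. The documents also do not say that earlier check-ups measured muscle in a comparable way.

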**2.3 Inclusion Criteria:**

- 2.3.1 Willingness to sign informed consent
- 2.3.2 Participation in the designated health check-up programs or prior pilot studies
- 2.3.3 Age  $\geq$  60 years (male or female)
- 2.3.4 Able to ambulate independently.
- 2.3.5 Meeting one of the following pre-sarcopenia criteria
  - Grip strength: <28 kg (men), <18 kg (women)
  - Walking speed: <1.0 m/s
  - Muscle mass: <7.0 kg/m^2 (men), <5.7 kg/m^2 (women)

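### Function and muscle mass are scheduled only at week 12 in a single supplemented group with no named baseline, and the metabolite 'before' sample is contradicted within the document, so the planned data cannot show a benefit

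*Combined protocol and SAP*

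**What the plan says.** **Function.** Section 1 says: "Functional assessments related to sarcopenia will be conducted after the intervention". Item 2.6.3 puts the "sarcopenia-related functional tests (body composition, grip strength, walking speed, and calf circumference") at the week-12 visit. Item 2.6.2 (week 6) lists blood, urine and adherence. The start is covered by 2.6.1: "Participants will undergo nutritional assessment via questionnaire and receive a daily supplement".

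**Entry.** Item 2.3.5 requires "Meeting one of the following pre-sarcopenia criteria", namely low grip strength, slow walking or low muscle mass. Item 2.3.2 requires "Participation in the designated health check-up programs or prior pilot studies", and 2.2 adds: "Those enrolled in the main integrated aging study and meeting inclusion criteria will be invited to participate". None of these gives a date for the qualifying reading or a maximum interval before the first sachet.

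**Samples.** Section 1 plans blood and urine "at two time points: mid-intervention (6 weeks) and post-intervention (12 weeks"). Item 2.7.1 counts two blood draws without dating them. Section 2.9 says, in the past tense, that samples were taken before and after supplementation.

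**Aim and analysis.** Using metabolomics, the sponsor states: "we aim to evaluate the effectiveness of nutritional supplementation, identify potential biomarkers for risk sarcopenia, and assess their prognostic value". The title says that nutrition ameliorates muscle loss. Section 2.10 plans paired t-tests of before against after, without naming variables. It also plans t-tests and ANOVA between groups that are defined nowhere.

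**The concern.** A claim that a supplement lessens muscle loss, or is effective, needs a change from a known starting value and something to compare that change with. For function and muscle mass the schedule gives a single reading, taken at the end. For metabolites the document gives two incompatible accounts of whether a starting value was collected. For neither is there an unsupplemented comparison.

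An analyst who needs a 'before' value for function will probably turn to the eligibility readings. Those had to be low on at least one measure for the person to enter, so some apparent improvement is expected even if the supplement does nothing. If instead the week-6 sample is used as 'before' for metabolites, the paired test compares two points on supplement and misses whatever happened in the first six weeks.

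**Working it through.** There is no planned figure to reproduce. Section 2.5 gives 120 participants without an effect size, SD, power or significance level. The check is therefore mainly a reading of the schedule.

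**1. What is measured when**

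| Source | Before first sachet | Week 6 | Week 12 |
|---|---|---|---|
| Functional tests, sections 1 and 2.6 | none listed | none listed | all four |
| Blood and urine, sections 1 and 2.6 | none listed | yes | yes |
| Blood and urine, section 2.9 | yes | not mentioned | yes |
| Blood draws, item 2.7.1 | two in total, undated | | |

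Scheduled functional time points: 1. Named or dated functional baselines: 0. Scheduled paired changes in function: none.

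**2. What the entry criteria guarantee.** Meeting one of three criteria guarantees one reading per person, on whichever measure qualified that person. The three criteria correspond to three of the four week-12 tests (muscle mass to body composition). Calf circumference is not an eligibility measure, so this document assures no earlier value of it for anyone. A full set of the other three is possible but not assured.

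**3. Whether the sampling statements can all hold.** Item 2.6.3 calls week 12 the second round of collection, which makes week 6 the first.
- Draws at weeks 6 and 12 only: fits section 1, 2.6 and 2.7.1, but contradicts 2.9.
- Draws before and after only: fits 2.7.1 and 2.9, but contradicts section 1 and 2.6.
- Draws before, at week 6 and at week 12: three draws, against two in section 1 and 2.7.1.
- Two draws here plus an earlier sample from the main study: all could hold, but the document does not say so.

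**4. Whether there is a comparison group.** Items 2.6.1 and 2.8 give the supplement to participants without distinction. No control, allocation or subgroup is described. The between-group tests in 2.10 therefore supply no control.

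**5. Illustration of regression to the mean, on assumed inputs only.** This applies only if qualifying readings serve as 'before'. Assume normal readings, a proportion q of the source population below the cut-off (15% to 30%), reliability r (0.80 to 0.95) and no true mean change. Among those who qualified on a measure, the expected false gain in population SDs is (1 − r) × φ(z_q) / q, where z_q is the normal quantile at q and φ the normal density.
- q = 0.15, r = 0.80: 0.20 × 0.2332 / 0.15 = 0.311 SD.
- q = 0.30, r = 0.95: 0.05 × 0.3477 / 0.30 = 0.058 SD.

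Averaged over all 120, including people who qualified on another measure, the gain is much smaller. Simulation with a further assumed correlation of 0.3 between measures gives about 0.01 to 0.09 SD. That average also assumes all three readings exist for everyone, which step 2 shows is not assured.

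**The case against.** The strongest reply has four parts.

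*The aim is metabolomic.* The effectiveness sentence in section 1 opens with metabolomics as its means, and the same section says functional assessments do not necessarily indicate sarcopenia itself. This stands. A reader might infer that the missing functional baseline alone defeats the effectiveness aim, but the wording does not support that. The sampling contradiction and the lack of a control bear on that aim more directly. The functional gap bears mainly on the title.

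*Baselines exist.* This is a subproject of a larger study whose records are not seen here. A reader might infer that no earlier functional value exists anywhere. That is not supported: a qualifying reading must exist, and the main study may hold a complete dated set. What stands is that none is designated here as the starting value.

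*A metabolite 'before' is specified.* Section 2.9 does specify one, so it would be too strong to say that the document gives no starting value at all. Nor can 2.7.1 be cited as confirming weeks 6 and 12, since it dates neither draw. The fault is a contradiction to be reconciled.

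*A single-arm exploratory study is legitimate.* It is. The criticism concerns the causal wording and the undefined groups. Within-person change during supplementation remains a proper thing to report where a baseline exists.

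**Conclusion.** The point holds. As scheduled, the study gives one reading of function and muscle mass, so no change can be estimated from it. Under sections 1 and 2.6 the paired metabolite tests have no pre-supplement sample, and 2.9 says otherwise. With everyone supplemented and no groups defined, neither a functional nor a metabolite change can establish effectiveness or a benefit on muscle loss. This rests on the text alone and needs no assumed figure.

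The size of any regression to the mean is unknown. The range of 0.06 to 0.31 SD among those who qualified on a measure depends wholly on assumed inputs. It should not be read as an estimate of bias in this study.

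The prognostic aim is affected less. An association between an earlier metabolite and week-12 function can be estimated without baseline function, but value beyond a person's current status cannot.

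**What to change.** 1. **Functional baseline.** If recruitment is open, add the four tests of 2.6.3 to 2.6.1, before the first sachet, and name them in 2.10 as the 'before' values for the paired t-tests. A fresh reading reduces regression to the mean and removes it only if its error is independent of the qualifying reading's error. If data collection is over, as the end date in 2.1 (May 31, 2023) and the past tense of 2.8 and 2.9 suggest, state the source and date of any functional baseline used, including one from the main study. Report change based on qualifying readings as subject to regression to the mean, and report no change for a measure without a baseline.
2. **Sampling times.** Reconcile sections 1, 2.6, 2.7 and 2.9, and state the source and date of the 'before' sample in the paired tests. If there is none, relabel the comparison as week 6 against week 12, both on supplement.
3. **Groups and wording.** Define the groups behind the between-group tests or delete those tests. Restate the aim as within-person change during supplementation, without 'effectiveness' or 'ameliorates'. Learning, seasonal and secular change remain mixed with any effect when there is no concurrent control.

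**Cost.** With recruitment open: a few minutes of non-invasive testing with equipment already used at week 12, and possibly one added visit. With collection over: wording only, and loss of the change analysis for measures without a dated baseline. Either way the claim becomes more modest. No extra participants are needed.

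### Section 1 promises the prognostic value of sarcopenia biomarkers, but the only biomarker analysis in section 2.10 is a concurrent association with unnamed health indicators

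*Combined protocol and SAP*

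**What the plan says.** Section 1 sets the objective: to "identify potential biomarkers for risk sarcopenia, and assess their prognostic value". It places sampling at "two time points: mid-intervention (6 weeks) and post-intervention (12 weeks" and adds: "Functional assessments related to sarcopenia will be conducted after the intervention".

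Section 2.6 gives the same timetable: "At week 6, participants will return for blood (5 mL) and urine (10 mL) collection and report supplement adherence" (2.6.2), then "At week 12, participants will return for a second round of blood and urine collection" (2.6.3). The week-12 visit also carries the "sarcopenia-related functional tests (body composition, grip strength, walking speed, and calf circumference". Section 2.7.1 counts two blood draws. Section 2.9 differs: it has blood and urine taken ahead of supplementation and again once it has ended.

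Section 2.10 plans PCA, t-tests, ANOVA and paired t-tests. Its one sentence on biomarkers says that metabolite changes will be "linked to individual health indicators to identify biomarkers associated with healthy aging".

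**The concern.** A prognostic claim needs a marker measured before the outcome that it is meant to predict. The predictor in section 2.10 is a change in concentration, and a change is not known until its second sample is taken. Here the second sample falls no earlier than the visit at which function is tested. A correlation obtained that way describes markers and function moving together. It does not show that a marker anticipates later function.

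The target also shifts between sections. Section 1 is about sarcopenia risk. Section 2.10 is about healthy aging, through indicators that it does not name, and neither sarcopenia nor prognosis appears in it. With metabolites from two biofluids and no fixed indicator, the choice of what to correlate with what stays open until the data are seen. Section 1 expects the findings to inform later monitoring of therapy, so a concurrent association taken for a prognostic one could mislead that work.

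**Working it through.** The plan gives no figure to reproduce on this point. The sample size of 120 comes without alpha, power or effect size, and the argument does not depend on it. The check is one of timing.

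**Inputs.** Functional outcome: week 12 (sections 1 and 2.6.3). Samples: weeks 6 and 12 (sections 1 and 2.6), or before and after supplementation (section 2.9). Blood draws: two (section 2.7.1). Supplementation: 12 weeks, for every participant (section 2.6.1).

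**Step 1: lead time of each sample.** Lead = week of functional outcome − week of sample.

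| Sample | Source | Lead to week-12 function |
|---|---|---|
| Pre-supplement (week 0), if taken | 2.9 | 12 − 0 = 12 weeks |
| Week 6 | 1, 2.6.2 | 12 − 6 = 6 weeks |
| Week 12 | 1, 2.6.3 | 12 − 12 = 0 weeks |

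**Step 2: lead time of the predictor that section 2.10 specifies.** A change is dated by its later sample.

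- Draws at weeks 6 and 12: the change is complete at week 12, so the lead is 12 − 12 = 0 weeks.
- Draws before and after supplementation: the change is complete at or after week 12, so the lead is at most 0 weeks.
- Pre-supplement to week-6 change: the lead would be 6 weeks. With the week-12 draw in 2.6.3, this needs three draws against the two counted in 2.7.1. Section 2.6.3 also calls the week-12 collection the second round, for urine as well as blood.

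No reading that respects the two-draw count puts the change before the outcome.

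**Step 3: which earlier level exists.** On the section 2.6 schedule, only the week-6 level precedes week-12 function. On the section 2.9 reading with two draws, only the pre-supplement level does. Either way there is one earlier level, with a lead of 6 or 12 weeks.

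**Step 4: entry values.** Section 2.3.5 admits a participant who meets one of three criteria: grip strength, walking speed or muscle mass. Section 2.6 schedules functional tests only at week 12. The plan does not say that all three measures are recorded at entry for everyone, so adjustment for the entry value cannot be taken for granted.

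**The case against.** The strongest reply is that the data described can support some prognosis. An outcome has to follow the predictor sample, not the last sample taken, and Step 1 shows a usable lead of 6 or 12 weeks. This stands. A reader might infer from the absence of any assessment after the last sample that the objective is unattainable; the documents do not support that. The gap is in the specified analysis and the stated target.

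Other replies also have force:

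- Section 2.10 gives no interval for the change, so a baseline-to-week-6 change might be meant. That would need a third draw, which 2.7.1 does not provide.
- The unnamed health indicators could include the week-12 functional tests. They could, but the text does not say so, and naming them is a simple repair. The healthy-aging wording is a mismatch of target and does not itself block an analysis.
- Later follow-up may exist in the parent aging study. These documents describe none, and nothing more can be said from them.
- Prognosis under supplementation is a legitimate question, given the interest in monitoring therapy. That is so, and the plan does not promise natural-history prognosis. It does mean that the claim must be confined to supplemented participants.
- Nothing says that a same-visit correlation will be labelled prognostic. That is right. The risk arises because the objective uses the word and section 2.10 offers no other analysis to answer it.

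**Conclusion.** The concern holds in this form: the prognostic objective has no named outcome, horizon or analysis, and the biomarker analysis that is specified is concurrent, with a lead of 0 weeks at best. What the design could support is an association over 6 weeks (from the week-6 sample) or 12 weeks (from a pre-supplement sample, if taken), under supplementation only.

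This rests on two blood draws per participant, on week 12 being the only functional assessment after entry, and on all participants receiving the supplement, as section 2.6.1 describes. If the sponsor confirms three draws, or follow-up through the parent study, the available lead times change and the plan should say so. The paired comparison of metabolites around supplementation is not affected by this point.

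**What to change.** 1. Reconcile the week-6 and week-12 schedule and two-draw count (sections 1, 2.6 and 2.7.1) with the before-and-after sampling in section 2.9. This comes first, because it decides which earlier sample exists.
2. In section 1, either delete the prognostic claim, or restate it as the association of the earlier metabolite level with week-12 function in supplemented participants.
3. If it is restated, add the analysis to section 2.10: regress week-12 muscle mass index, grip strength and walking speed, each in turn, on the earlier metabolite level, adjusting for the entry value of the same measure where recorded. Confirm whether all three are recorded at entry for every participant. They are chosen because section 2.3.5 already uses them to define pre-sarcopenia; calf circumference is not an entry criterion.
4. In section 2.10, name these measures in place of the unspecified health indicators and the healthy-aging target, and label any result relating metabolite change to week-12 function as a concurrent association.

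The cost is rewording, a small amount of prespecified analysis and a check on entry data. No additional participants are needed. The drawback is a weaker claim, limited to a short horizon under supplementation.
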